5.9.3 Randomization Scheme

Randomization to intervention (SOC and full CARE+ Prevention counseling session) or control arm (SOC alone) is done automatically within the software application using a pseudo-random number generator.

5.9.4 Data Analysis

Data to be analyzed for this study component will be obtained from the CARE+ electronic storage system and abstracted from participant's medical records. As participants proceed through the CARE+ intervention, their answers will automatically be stored electronically in a secure system. Access to the storage system will be limited to essential personnel. CD4 cell counts and HIV RNA levels obtained from month 0 through month 12, will be extracted from participant's medical records to enable individual-level subgroup analyses of adherence and virologic responses among CARE+ participants who are receiving versus not receiving FIs for virologic suppression, as well as other subgroup analyses.

The primary behavioral endpoint of this study component is the proportion reporting any unprotected vaginal or anal sex the last time they had sex.

Effectiveness of the CARE+ Prevention for Positives component will assess differences in proportion reporting self-reported risk behavior for participants in the CARE+ Prevention arm compared to the control arm. GEE methods for repeated measures will be used to assess the difference in proportion reporting high-risk behavior between the two study arms for participants. Major subgroup analyses for those on ART and not on ART will be conducted.

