4.5 Intervention for Viral Suppression

HIV-positive individuals at HIV care sites assigned to the FI intervention will receive FIs (gift cards worth \$70) to reinforce adherence to ART as measured by confirmation of each suppressed VL measurement (<400 copies/mL). The gift cards will be distributed at the HIV Care sites during each routine, quarterly clinic visit that a study participant demonstrates a suppressed VL.

In the event participants report full adherence to their providers but have not succeeded in achieving VL suppression, providers will be expected to obtain resistance testing, as recommended by current treatment guidelines, and to alter their patients' regimens accordingly. Once patients with resistant HIV are on appropriate regimens, they will again be eligible for FIs for viral suppression. The specific procedures for HIV care sites to distribute the FIs for viral suppression will be outlined in the HPTN 065 SSP.

This intervention will be compared to SOC support for ART adherence through the use of routinely collected HIV surveillance data.

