4.6.1 Monitoring HIV Care Sites

It is possible that members of the intervention communities, particularly those who are HIV-positive, will learn of the FI intervention to promote viral suppression and seek out HIV care sites offering these incentives. In an effort to minimize significant migration of patients from HIV care sites without FIs to ones that offer them, the following rules have been put into place:

- A patient must have at least one VL measurement at the HIV care site between three and nine months prior to the first suppressed VL for which he or she may receive an incentive. Both of these VL measurements must be done at the same HIV care site.
- All subsequent VL measurements for which a patient may receive FIs must be performed at the same HIV care site.

If a patient changes HIV care sites during the course of the study, he or she will be required to "establish care" at the new HIV care site prior to receiving any FI for a suppressed VL as indicated above. Specifically, to receive an FI again, the individual must have a VL measurement at the new HIV care site and return in three to nine months for a repeat VL measurement. The results of the second test will determine whether the person receives the FI or not.

Despite this barrier to HIV-care-site migration, the FI intervention may encourage this phenomenon; thus, the study team will use surveillance data to monitor the case load at each site at frequent intervals. By monitoring HIV care site case load over time, the team will be able to determine if significant migration is taking place. This will motivate discussions with the community advisory group to design other mechanisms to minimize such migration or if needed a redesign of this component of the study may be embarked on by the study team.

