4.8.3 Randomization Scheme

In the viral suppression study component, facilities that provide HIV care services (HIV care sites) will be randomized to use FIs or the SOC.

HIV care sites will be assigned to one of the following two arms:

- Sites offering FIs for VL suppression: FIs offered to all those who are on ART, upon the confirmation of each suppressed VL measurement (<400 copies/mL)
- Sites continuing with SOC to encourage VL suppression: Each person on ART will be offered support via the site's SOC procedures to attend HIV care site visits and remain adherent to their ART regimen in order to achieve and maintain VL suppression

The site randomization will be balanced by the following two baseline characteristics:

- The size of the site's HIV-positive patient case load
- The proportion of HIV-positive patients with VL suppression at each site

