5.4 Study Sites for Prevention for Positives

Participants will be recruited for the Prevention for Positives component of the study from six HIV care sites (three FI sites and three SOC of care sites) in each intervention city.

The three sites among the FI sites and the three sites in the SOC sites in each city will be selected based on the following criteria:

- The highest volume of HIV-positive patients in care
- Site agreement to participate in this component of the study

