5.5 Intervention for Prevention for Positives

A modified version of CARE+ for HIV-positives will be used with Audio Computer Assisted Self-Interviewing (ACASI) to measure behavioral risk and to compare a full computer counseling intervention (assesses self-efficacy and motivation, provides tailored feedback on specific risk behaviors, shows skill-building videos, and helps the user make a risk-reduction plan) to a control session consisting only of ACASI ascertainment of risk behavior.

An additional component will be the utilization of the computer-based system described above to measure factors that impact both the acceptability of the interventions utilized in this study and the feasibility of future TNT strategies. Other data, beyond those that can be obtained from routine HIV surveillance data, will be captured including the following:

• HIV testing history and prior experience with linkage/drop out from care (if applicable)

- CD4 cell count (via chart abstraction, not routinely available from HIV surveillance), at study enrollment, and then every 3 months up to and including month 12
- VL (via chart abstraction, not routinely available from HIV surveillance), at study enrollment, and then every 3 months up to and including month 12

CD4 cell counts and HIV RNA levels obtained from month 0 through month 12, will be extracted from participant's medical records to enable individual-level subgroup analyses of adherence and virologic responses among CARE+ participants who are receiving versus not receiving FIs for virologic suppression, as well as other subgroup analyses, such as:

- Behaviors likely to transmit HIV (sexual and parenteral)
- Receipt of and experience with services to promote retention and adherence
- Knowledge of, attitudes towards, and the feasibility of early initiation of ART
- Knowledge of and attitudes towards use of ART for prevention in partners

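### The CARE+ subgroup comparison by receipt of the viral-suppression incentive, read literally, lets the outcome define the groups; it should be worded by the care site's randomised arm

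*Protocol*

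**What the plan says.** Protocol 5.9.4 states why CD4 counts and HIV RNA are taken from the charts of CARE+ participants from month 0 to month 12: to enable subgroup analyses, at the level of the individual, of "adherence and virologic responses among CARE+ participants who are receiving versus not receiving FIs for virologic suppression, as well as other subgroup analyses". Section 5.5 gives the same purpose in the same terms.

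The conditions for payment are in section 4:
- 4.5: the gift card is handed out "during each routine, quarterly clinic visit that a study participant demonstrates a suppressed VL", with suppression set at below 400 copies/mL.
- 4.6.1: an earlier viral load at the same site is needed before a first payment. For a patient who changes site: "The results of the second test will determine whether the person receives the FI or not".
- 4.8.3, describing the incentive arm: "FIs offered to all those who are on ART, upon the confirmation of each suppressed VL measurement".
- 4.1 treats patients on ART as eligible for incentives, and lists receiving them separately, as something that follows suppression.

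Two further provisions matter. Section 5.3 admits participants who are not on ART. Section 5.4 recruits from "six HIV care sites (three FI sites and three SOC of care sites) in each intervention city", so each participant's site has a randomised FI or SOC assignment.

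**The concern.** Read literally, the comparison groups participants by a variable that the response itself determines. Everyone counted as receiving has been suppressed at least once. Those not receiving are a mixture: all participants at SOC sites, suppressed or not, and the FI-site participants who were never paid, including those never suppressed and those not on ART. The earlier-measurement rule in 4.6.1 also tilts the receiving group towards patients retained at one site.

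Such a comparison shows better virologic response among receivers even if the incentive does nothing. Adherence would be pulled the same way so far as it goes with suppression, though that part is not quantified here. These are the data abstracted for individual-level virologic subgroup analyses in CARE+, in a study meant to inform a later community-level trial. A gap several times the planned effect could be mistaken for supporting evidence on incentives.

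**Working it through.** The Protocol gives no sample size, power or expected difference for this comparison, so there is no figure of its own to reproduce. The check sets the incentive effect to zero and asks what gap the grouping alone creates.

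**Inputs from the Protocol**
- Suppression: 60% (SOC design value, 4.8.2), 57% (Bronx, 2008), 67% (Washington, D.C., 2008).
- Sites: 3 FI and 3 SOC per city (5.4), so 6 versus 6. About 110 participants per site (5.9.2): 12 × 110 = 1320, or 660 per FI/SOC group, half at FI sites.
- Between-site ICC of suppression: 0.07 (Bronx) and 0.104 (D.C.), 4.8.2.
- Planned effects: 60% to 66% or 70% (Table 3), that is 6 to 10 points.

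**Assumption, not in the Protocol:** within-person correlation of suppression across quarters of 0.3, 0.5 or 0.8.

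**1. Extreme case: payment at the same visit, or suppression fixed within person.** With suppression probability p and half the participants at FI sites, receivers make up 0.5p of participants and are all suppressed. Suppression among the rest is 0.5p / (1 − 0.5p).
- p = 0.60: 0.30 / 0.70 = 42.9%; gap 57.1 points.
- p = 0.57: 0.285 / 0.715 = 39.9%; gap 60.1 points.
- p = 0.67: 0.335 / 0.665 = 50.4%; gap 49.6 points.

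**2. Ever paid.** One million persons were simulated per setting, with a beta-binomial suppression probability and quarterly values to month 12. Receipt means any suppressed value in months 3 to 12 at an FI site; the outcome is suppression at month 12.

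| Suppression | Correlation | Receiving | Not receiving | Gap (points) |
|---|---|---|---|---|
| 57% | 0.3 | 65.8% | 50.2% | 15.6 |
| 57% | 0.5 | 72.5% | 46.9% | 25.6 |
| 57% | 0.8 | 86.5% | 42.6% | 43.9 |
| 60% | 0.3 | 67.9% | 53.8% | 14.1 |
| 60% | 0.5 | 74.2% | 50.5% | 23.7 |
| 60% | 0.8 | 87.4% | 45.7% | 41.7 |
| 67% | 0.3 | 72.7% | 62.0% | 10.8 |
| 67% | 0.5 | 78.1% | 58.7% | 19.4 |
| 67% | 0.8 | 89.5% | 53.5% | 35.9 |

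**3. Earlier payment only (months 3 to 9) against month-12 suppression.** The lag does not remove the gap. At 60% suppression it is 10.8 points (66.3% vs 55.5%), 21.3 (73.1% vs 51.8%) and 40.8 (87.1% vs 46.3%) for correlations 0.3, 0.5 and 0.8. The smallest value over all settings is 8.6 points (71.7% vs 63.1%, at 67% and 0.3), which falls inside the planned range.

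**4. Grouping by site arm.** In the same simulations the arms agree to within about 0.2 points, that is, no difference beyond simulation noise.

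**5. Precision of the site-arm contrast.** Design effect = 1 + 109 × ICC; SE = √(2 × 0.6 × 0.4 × design effect / 660); t on 10 df (2.228).
- ICC 0.07: design effect 8.63, SE 7.9 points, 95% half-width 17.7 points, detectable difference at 80% power 24.6 points.
- ICC 0.104: design effect 12.34, SE 9.5 points, 95% half-width 21.1 points, detectable difference 29.4 points.

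**The case against.** The strongest reply is that clinic arm was meant. The Protocol elsewhere describes randomised arms as receiving one thing or another. The deliberate choice of three FI and three SOC sites per city suits a comparison by arm. Payments are recorded in tracking logs that reach the study team without identifiers (4.8.4), and no section plans to link them to CARE+ participants. This reading is plausible, and under it the bias disappears. It is not what the text says, however, and 4.1 uses receipt for payment after suppression. The wording needs settling either way.

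A second reply is that a subgroup analysis could mean CARE+ against control within strata of receipt. The gaps above would then not apply. The strata would still be defined after randomisation by the response under study, and site arm would be the sounder stratifier.

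A third is that this is exploratory: 5.9.1 lists no virologic endpoint, the comparison has no stated sample size or decision role, and a subgroup's exact definition can be left to an SAP, which is not at hand. That lowers the weight of the point. It does not remove it, because the Protocol itself names the grouping.

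A reader might also infer that the trial leaves its randomised incentive comparison unused. It does not: 4.8.4.1 makes it the Viral Suppression primary analysis, over 40 sites, by intention to treat, with within-person and within-clinic correlation.

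**Conclusion.** The point holds as a defect of wording in an exploratory analysis. If groups are formed by actual payment, the comparison carries a built-in benefit under the null: about 11 to 44 points for ever-paid grouping, conditional on the assumed within-person correlation, and 50 to 60 points in the extreme case. All of these exceed the planned 6 to 10 points; with payment lagged, the mildest setting (8.6 points) is of similar size to the planned effect.

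Two stronger conclusions are tempting and not supported. One is that the trial will report a false incentive effect: that requires the payment reading, which the text suggests but does not establish. The other is that the false gap will be near 57 points: that is the extreme case, not the expected one. The CARE+ primary endpoint and the Viral Suppression primary analysis are untouched. The text should be corrected, but the main conclusions do not depend on it.

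**What to change.** In 5.5 and 5.9.4, replace the wording that groups participants by receipt with *enrolled at care sites randomised to FI versus SOC*. Fix the group by site at enrolment, include every participant whether or not ever paid and whether or not on ART, and account for clustering by the 12 sites within city. Report actual receipt only as a descriptive uptake figure. Label the comparison exploratory and refer to the Viral Suppression primary analysis for the incentive's effect.

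The cost is a change of wording in two sections, carried into the SAP; no new data are needed. The price is precision: a 95% half-width of about 18 to 21 points cannot resolve effects of 6 to 10 points. The revised contrast is free of the outcome-defined bias provided that enrolment into CARE+ does not differ by site arm. Participants consent individually, possibly after incentives have begun, so baseline characteristics should be shown by site arm.

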Linkage-to-Care: HIV test sites will be randomized to either the FI intervention or to the SOC for linkage of HIV-positive patients identified at the testing sites to HIV care sites. At HIV test sites assigned to FIs, HIV-positive patients will be provided with a coupon to redeem at participating HIV care sites in the community. Upon completion of HIV laboratory testing, patients with coupons will be given an FI (\$25 gift card) at an HIV care site. A \$100 gift card will be provided to patients upon completion of a care visit that includes interaction with a healthcare provider and discussion of HIV laboratory test results (*e.g.* CD4 cell count and viral load (VL) measurements).

Viral Suppression: HIV care sites will be randomized to either the FI intervention or the SOC for the achievement and maintenance of viral suppression. HIV care sites assigned to the FI intervention will provide an FI (\$70 gift card) to HIV-positive patients on antiretroviral therapy (ART) demonstrating a suppressed VL (as defined by <400 copies/mL) at quarterly care visits.

Prevention for Positives: In a subset of patients enrolled from select HIV care sites in the two intervention communities, patients will be randomized either to an intervention arm (receiving SOC prevention activities plus a computer-delivered intervention for sexual and behavioral risk reduction) or to the control arm (receiving only the SOC prevention activities at the care site). In the intervention arm a modified version of the computerized counseling platform called Computer Assessment and Risk Reduction Education for HIV-positives (CARE+) will be used with an Audio Computer Assisted Self-Interviewing technique (ACASI). The CARE+/ACASI intervention session will ascertain behavioral risk, assess self-efficacy/motivation, and provide tailored feedback on specific risk behaviors. The computer-delivered intervention session will also have CARE+/ACASI sessions every three months. However, participants in the control arm will only be administered behavior assessments via CARE+/ACASI and will not receive prevention messaging.

TLC-Plus: A Study to Evaluate the Feasibility of an Enhanced Test, Link to Care, Plus Treat Approach for HIV Prevention in the United States

SCHEMA (Continued)

Study Components (continued):

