5.7 Study Duration for Prevention for Positives

Duration of the Prevention for Positives study component is 12 months.

Patients enrolled in the Prevention for Positives component of the study will complete the CARE+/ACASI tool at baseline (month 0) and every three months thereafter for one year (at months 3, 6, 9, and 12).

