5.9.2 Accrual, Follow-up, and Sample Size

The primary behavioral endpoint of this study component is the proportion of patients reporting any unprotected vaginal or anal sex the last time they had sex. In the Strategies for Management of Antiretroviral Therapy (SMART) study, at 11.2% of visits participants reported any unprotected anal or vaginal sex in the previous two months. Using post-enrollment data; 5.4% of patient visits included a report of unprotected anal or vaginal sex with an HIV-uninfected partner in the previous two months.

Individual randomization will occur, potentially stratified by gender.

Using a 2-sided alpha of 5%, and calculating the sample size required to achieve 90% power to detect differences in percentages of participant visits where high-risk behaviors are reported in each arm, Table 4 presents a number of assumptions. A within-person, ICC of 0.3-0.4 is assumed, based on data from the SMART trial behavioral endpoints.

Assuming at least one follow-up visit for 90% of enrollees, and an average number of visits per participant of 3.75 amongst retained participants, the study will enroll 660 per arm (1320 in total) to allow for loss due to attrition and loss to follow-up. It is estimated that around 110 participants will be recruited per HIV care site, with a target enrollment of two subjects/day per site. Target enrollment should be reached within eight-12 months of initiation, and accrual will be terminated at 1320 participants or after approximately 12 months of accrual, whichever occurs first.

It is anticipated that a total of approximately 1320 individuals will be randomized. Data will be collected from each person an average of 4 times during the study (out of four possible visits following enrollment at month 0, *i.e.* months 3, 6, 9, and 12). Allowing for

loss to follow-up, with 522 people available for assessment per arm, the study has 90% power to detect a decrease from 11% to 8% in proportion of patients reporting any unprotected vaginal or anal sex at a given visit during the study.

Control (%)	Intervention (%)	Mean Number of Visits	Intra-class Correlation	Number of People per Arm	Intra-class Correlation	Number of People per Arm
5.4%	3.0%	4	0.4	378	0.3	373
5.4%	3.5%	4	0.4	638	0.3	630
5.4%	4.0%	4	0.4	1240	0.3	1223
7.5%	4.0%	4	0.4	243	0.3	238
7.5%	4.5%	4	0.4	344	0.3	337
7.5%	5.0%	4	0.4	515	0.3	505
11%	7.5%	4	0.4	385	0.3	374
11%	8.0%	4	0.4	537	0.3	522
11%	8.5%	4	0.4	792	0.3	769

 Table 4:

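### The Prevention for Positives primary GEE is stated without the month 0 value of the same risk behaviour. Adding it is a nearly free efficiency gain, but its size depends on what the plan's 0.3-0.4 correlation really is.

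*Protocol*

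**What the plan says.** Section 5.7 of the protocol says that enrolled patients "will complete the CARE+/ACASI tool at baseline (month 0) and every three months thereafter for one year". Appendix I shows the same schedule. The Schema states that control participants also receive the behaviour assessment, without the prevention messages. The risk behaviour is therefore due to be recorded at month 0 in both arms.

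Section 5.9.2 bases the sample size on the four visits after enrolment (months 3, 6, 9 and 12). On correlation it says "A within-person, ICC of 0.3-0.4 is assumed, based on data from the SMART trial behavioral endpoints". It claims 90% power for 11% versus 8% with 522 assessable people per arm.

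On allocation, Section 5.9.2 says "Individual randomization will occur, potentially stratified by gender", and Section 5.9.3 adds that it "is done automatically within the software application using a pseudo-random number generator". Section 6.5 places randomisation after the participant logs in.

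The primary analysis in Section 5.9.4 is: "GEE methods for repeated measures will be used to assess the difference in proportion reporting high-risk behavior between the two study arms for participants". No covariate, working correlation or time term is given, and the role of month 0 is not stated. The linkage and viral suppression sections (3.8.4, 4.8.4 and 4.8.4.1) refer some analysis details to the statistical analysis plan. Section 5.9.4 does not.

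**The concern.** The endpoint is uncommon, about 11% in the control arm. If answers from the same person are correlated at 0.3-0.4, much of the noise in the arm comparison comes from lasting differences between people in risk. A measurement of the same behaviour before counselling removes part of that noise. An analysis that leaves it out has a wider confidence interval and a greater chance of missing a real reduction. Section 5.9.4 credits neither this value nor gender, the one stratification factor mentioned. At stake is precision in the trial's only individually randomised comparison, using data the trial already plans to collect.

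**Working it through.** **Inputs, all from Section 5.9.2:** two-sided 5%; 11% versus 8%; m = 4 follow-up visits; 522 per arm; ICC 0.3 or 0.4. The retention case is 90% of 660 = 594 per arm with 3.75 visits.

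**1. The plan's own figure.** Table 4 gives 522 (0.3) and 537 (0.4) per arm for 90% power.
- *Read as an ICC.* The two-proportion size multiplied by (1 + 3·ICC)/4 gives 953 and 1,103 per arm. This does not match.
- *Read as a coefficient of variation k.* n = 1 + (1.96 + 1.2816)² × [(0.0979 + 0.0736)/4 + k²(0.0121 + 0.0064)]/0.03² gives 521.0 and 536.1. All 18 cells of Table 4 agree with this formula to about one person.

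So the table treats as a coefficient of variation what the text and column heads call an ICC. That is a separate error, but it decides the starting power used below.

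**2. Power without month 0, reading 0.3-0.4 as an ICC.** SE² = [(1 + 3·ICC)/4] × 0.1715/522.
- ICC 0.3: SE = 0.01249; power = Φ(0.03/0.01249 − 1.96) = 67.1%.
- ICC 0.4: SE = 0.01344; power = 60.7%.

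**3. Power with month 0 as a covariate.** If month 0 correlates with each follow-up visit at the same ICC, the variance of the person mean that it explains is R² = ICC²/[(1 + 3·ICC)/4].
- ICC 0.3: R² = 0.09/0.475 = 0.189; power 76.0% (+9 points).
- ICC 0.4: R² = 0.16/0.55 = 0.291; power 75.5% (+15 points).
- 594 per arm and 3.75 visits: 71.6% to 80.0%, and 65.5% to 79.7%.

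Simulated beta-binomial data at 522 per arm, analysed by logistic GEE with robust errors (2,000 trials per setting), gave 70.5% to 78.5% and 66.0% to 77.6%. Under no effect, rejection was 5.8% unadjusted and 6.0% adjusted at ICC 0.3, and 4.2% and 5.1% at ICC 0.4.

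**4. How the gain changes with the assumptions.**

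| Assumption | Gain in power |
|---|---|
| ICC 0.3-0.4, month 0 equally correlated, base 67% / 61% | 9 / 15 points |
| Same R², starting from the plan's 90%: Φ(3.2416/√(1 − R²) − 1.96) = 95.0% / 97.1% | 5 / 7 points |
| Month 0 correlation 75% of the ICC (0.225 / 0.30) | 5 / 8 points |
| Month 0 correlation only 0.15-0.20 | about 2-4 points |
| 0.3-0.4 is a coefficient of variation: implied ICC = k² × 0.11/0.89 = 0.011 / 0.020, R² = 0.0005 / 0.0015 | about 0 |

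**The case against.** The strongest reply is that Section 5.9.4 fixes only the method, GEE, and is silent on everything else. Model covariates are commonly left to a statistical analysis plan, which may exist but was not available here. A repeated-measures GEE that uses month 0 would be consistent with the sentence as written. This stands: a reader might infer that the protocol chose to discard baseline, but the text does not say so. What can be said is narrower. The analysis as stated does not include month 0, the sample size gives it no credit, and Section 5.9.4 has no pointer to a later document. By contrast, Section 4.8.4.1 does name its stratification by city.

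Four further replies also stand.
- **Base power.** The gain of 9-15 points starts from 61-67%, not from the 90% the plan claims, so it cannot be quoted alone as the plan's own loss.
- **Borrowed correlation.** The ICC comes from the SMART study, whose rates quoted in Section 5.9.2 concern the previous two months. The endpoint here concerns the last time the participant had sex. No month 0 to follow-up correlation is given for it.
- **Completeness and order.** Section 5.8 lets participants skip questions, so a month 0 value is not assured for everyone. Randomisation happens at login, so month 0 answers are recorded after allocation. The Schema says "The CARE+/ACASI intervention session will ascertain behavioral risk, assess self-efficacy/motivation, and provide tailored feedback on specific risk behaviors", which suggests that risk is asked before feedback but does not establish it.
- **Validity.** A reader might infer that chance imbalance biases the unadjusted result. It does not. Over randomisations the contrast is unbiased, its standard error already covers such imbalance, and the simulated error rates in the working are close to nominal.

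**Conclusion.** This is an efficiency improvement, not the correction of a bias or of a wrong statement. Adjusting for month 0 would add about 9 points of power (ICC 0.3) or 15 points (ICC 0.4) at 522 per arm only if 0.3-0.4 is a real exchangeable correlation that holds equally between month 0 and follow-up. Weaker correlation or a higher starting power shrinks the gain, and under the coefficient-of-variation reading it nearly vanishes. The document cannot settle which case applies. The recommendation does not depend on the answer: with a positive correlation the adjustment helps, and with almost none it costs practically nothing at this sample size. The mislabelled correlation in Table 4 matters more. If the ICC label is right, power at 522 per arm falls about 23-29 points short of the claimed 90%. Baseline adjustment recovers part of that shortfall but does not repair it.

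**What to change.** State in Section 5.9.4, or there by reference to the statistical analysis plan, that:
- the primary GEE is fitted to months 3, 6, 9 and 12, with the participant's month 0 value of the same endpoint and visit as covariates, plus gender if randomisation is stratified by it;
- the month 0 value comes only from risk questions asked before any feedback, and the protocol confirms that order in both arms, because allocation occurs at login;
- a category for no sex, skipped or missing at baseline keeps every participant in the model;
- the arm effect is reported as a marginal (standardised) difference in proportions with robust standard errors, so that the quantity estimated remains the difference in Section 5.9.4;
- the unadjusted GEE is kept as a sensitivity analysis.

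The cost is a few lines of text, a standardisation step and one extra baseline category. No new data, visits or staff are required. If the statistical analysis plan already specifies this, a cross-reference is enough.
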